Rather than an alternative medium for implementation of existing interventions designed for in-person contact, social media may be a true 'game changer'^{74,76,77,121,122} to engage hard to reach individuals. While many online behavioral interventions exist, including some that use social media,¹⁶⁹ ours will be the first to use social media to facilitate uptake of a biomedical intervention. E-PrEP will connect the target population (YMCSM) to a new prevention tool (PrEP) through rapid linkage to medical care, accelerating diffusion of PrEP. Given the paucity of data regarding social media-based interventions to change health-related behavior, E-PrEP may have a marked impact on future bio-behavioral interventions, especially those that include diffusion of innovation.

Social media offers the power of scale and efficiency for large potential impact, even with relatively low intensity interventions.^{77,109,122} Similarly, PrEP, if widely adopted in high-risk populations and offered with behavioral interventions, could markedly decrease HIV infection rates. Social media-based, peer-led approaches like E-PrEP could be used to enhance efforts by community based and other organizations that employ internet-assisted or peer-outreach strategies to improve health.⁷⁶

Aims: To test the feasibility and preliminary efficacy of E-PrEP for increasing PrEP adoption in a cluster-randomized controlled trial.

Methods

Participants: The 16-20 peers will be randomized 1:1 to either E-PrEP or BxNow (control condition). They will then recruit n=240 total participants (120 for E-PrEP and 120 to BxNow). Each Peer will recruit approximately n=15 participants.

Inclusion criteria: Male or trans individuals; Ages 18-29; Have had unprotected anal sex with a male partner in the prior 12 months; Fluent in English or Spanish; Are HIV negative or unknown status (self-report); Identify as Black and/or Latino

Exclusion criteria: YMCSM or trans individuals who do not consent/assent to study; Are currently taking PrEP for HIV prevention, not currently using at least one of 3 social media sites that will be used for the E-PrEP intervention (e.g. not using Facebook, Twitter, Tumblr).

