Intervention Procedures: After target enrollment (n=240) is reached, YMCSM Peers will begin the intervention by posting materials according to the timeline developed in the ongoing E-PrEP content project. We will hold weekly project meetings (on different days) with Peers assigned to both E-PrEP and BxNow to ensure appropriate implementation, and to discuss logistical, ethical, or other issues that arise. For participants in the BxNow control arm, Peers will post about general health topics unrelated to HIV or sexual health (e.g. fitness, nutrition, smoking). If a control participant posts a question about PrEP, Peers will refer the individual to the CDC PrEP information site or answer the question privately. Content for both arms will be posted over a 6 week period, and outcome data will be collected via online surveys at baseline, 6, and 12 weeks and after 36 weeks (Table 13). Participants will be given \$20, \$30, and \$40 and 20 online gift-cards or through a Clincard as incentives after completion of assessments at T1, T2, and T3, and T4 respectively.

Anticipated components of E-PrEP: Potential components are listed in Table 2. *However, the exact contents, formats, and mode and timing of delivery of E-PrEP will be informed by input from Peers.*¹²³ We have successfully used this approach in *theSEXword* pilot, with ongoing engagement by participants. We will develop all components for both E-PrEP and the control condition (BxNow), and will also create an intervention activity guide for all 6 weeks, but the exact timeline for intervention delivery will be determined based on findings from Aims 1 and 2. We will thus standardize E-PrEP in its mode of delivery, types of digital media and contents, message framing, and sequence of topics posted and discussed, but Peers will tailor the exact language of posts based on their communication style. Components will be interactive wherever possible; for example, to target a factor such as perceived low risk, participants might assess their risk in an interactive poll, see results in real-time, compare themselves to others, and be engaged by Peers in discussions about risk. To address barriers to access, we might develop a brief time-elapsd video showing where and how to register at a clinic to obtain PrEP. All materials, including assessments, will be smartphone friendly, as most participants use mobile devices.

Table 1. Intervention Timeline

Component	Week	-4	0	6	12	36+
Participant Recruitment						

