1. <https://www.qualtrics.com/support/survey-platform/survey-module/survey-options/survey-protection/#PreventingRespondentsFromTakingYourSurveyMoreThanOnce>

Furthermore, we will download the raw data and store it in a password protected *and* encrypted file on the office computer of [name]. Only the PIs and research study staff will have access to the full data-set.

Analytic Plan: Our *primary outcome* will be *intention to use PrEP*,⁸³ which we consider a predictor of subsequent use,¹⁴² and will be measured using a Likert scale. We will use ‘intention’ as a proxy given the low likelihood of actual PrEP use.^{83,132,143} *Secondary outcomes* will be PrEP use, knowledge,¹⁴³ perceptions about PrEP¹³⁴ and HIV testing- and risk-behaviors.¹⁴⁴ *Covariates*^{80,81,143,145-148} will include access to medical care (including HIV/STI testing), sexual orientation, HIV and PrEP related stigma, substance use, sociodemographic factors,¹⁴⁴ social media engagement and network data,^{149,169} and perceived affinity to the referring Peer.¹⁵⁰ First, we will compare groups for equivalence at baseline, using chi-square or t-tests as appropriate. In addition, we will determine whether subgroups (e.g., grouped by number of social media sites joined, social media platform(s) used, peer referent, race/ethnicity, and sexual orientation) differ with respect to the primary and secondary outcomes. Relevant differences will be used as covariates in subsequent models. At each time point, we will examine change in our primary outcome variable (*intention to use PrEP*) by using a traditional two-sample test of proportions. To compare differences in outcomes between arms over time, we will use

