repeated measures mixed-effects logistic and linear models, with the treatment arm as a fixed-effect, Peers as a random-effect, and time (as a linear term) as an independent variable. We will also look at residual plots to determine if we need to include non-linear terms for time. Next, we will use hierarchical models to examine the role of secondary outcomes as potential mediators of change over time, e.g. are there differences by condition in PrEP knowledge or perceptions that account for differences in intentions. Finally, we will assess the impact of the exposure arm (E-PrEP or BxNow) and selected covariates (significant in the bivariate analysis at $p < 0.1$) on the primary and secondary outcomes using mixed-effects models. We will also assess the impact of online process and engagement variables on outcomes. To overcome possible limitations due to intra-cluster correlations, we will include a modified sensitivity analysis that examines outcomes in relation to participants' network size and perceived affinity to the Peers. To test *feasibility*, we will assess online process measures, including participation rate (# of individuals screening eligible and then ultimately joining the study), engagement activity (e.g. time spent viewing posted videos, # of responses posted to questions, participation in polls, etc.), and retention (# of participants actively 'leaving' or 'un-joining' a social media study site and # of respondents to follow-up assessments).

Power Analysis: The primary purpose of this study is to test feasibility and to obtain an effect size estimate for a future R01 application. We estimate that a sample size of 220, accounting for up to 20% attrition¹⁰⁶ will provide 80% power to detect an effect size of 20% in E-PrEP vs. 5% in BxNow in the proportion of participants indicating '*intention to use PrEP*' at 6 weeks, with a two-sided $\alpha < .05$. We will also have adequate power to detect a smaller effect size at 12 weeks because of our repeated measures design. This conservative effect size estimate is reasonable, given the novelty of the proposed intervention, the absence of other studies assessing uptake of a biomedical tool in YMSM, and the results of other studies assessing potential interest in PrEP.⁸³

Procedures outlined below have been guided by [name] (Consultant), and by [name] (Consultant), who has extensive experience in conducting online survey and intervention studies with vulnerable populations including MSM.

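### The over-time models name no Peer-by-time random effect, so on the ordinary reading Peer-to-Peer variation in response is missing from the standard error of the arm-by-time contrast

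*Combined protocol and SAP*

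**What the plan says.** Peers are the randomised unit: 16 to 20 of them, 1:1, under Methods and under Recruitment for general participants (Section I.1.2 says 16). On cluster size, "Each Peer will recruit approximately n=15 participants", for 240 in all. Peers also deliver the content. The section on anticipated components standardises the mode of delivery, media, framing and order of topics, "but Peers will tailor the exact language of posts based on their communication style".

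The Analytic Plan introduces the longitudinal analysis with the words "To compare differences in outcomes between arms over time, we will use". The model family that it then names is "repeated measures mixed-effects logistic and linear models". The terms in these models are given as "with the treatment arm as a fixed-effect, Peers as a random-effect, and time (as a linear term) as an independent variable". On the shape of time it adds: "We will also look at residual plots to determine if we need to include non-linear terms for time". On intra-cluster correlation it adds: "we will include a modified sensitivity analysis that examines outcomes in relation to participants' network size and perceived affinity to the Peers".

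The plan does not write out an arm-by-time term, a participant random effect, a Peer slope or Peer-by-visit effect, a cluster-robust standard error, small-sample degrees of freedom, or any ICC.

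**The concern.** A random effect for Peer with no time term attached describes how groups differ at every visit alike. A comparison of change subtracts it out. What remains uncertain at Peer level is how much each group moves, and the named structure has no term for that. Participants' changes are then treated as independent within a Peer's group, although the Peer was randomised and leads the discussion.

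The two further steps in the plan do not fill the gap. The residual-plot check concerns the mean trend only. The sensitivity analysis relates outcomes to two covariates and adds no variance component for change.

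At stake are the false-positive rate and the interval for the over-time arm effect. The Power Analysis says that the study is meant to supply an effect-size estimate for a later application, so a wrong interval would carry into that planning.

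**Working it through.** **The plan's own figure.** The Power Analysis gives 220. The two-proportion formula for 20% versus 5%, two-sided 0.05 and 80% power gives 76 per arm, or 88 with a continuity correction. Then 2 × 88 = 176, and 176/(1 − 0.20) = 220. The figure is reproduced. It has no allowance for clustering and concerns proportions at week 6, so it does not size the over-time contrast.

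**Linear model, full enrolment.** From the documents: 16 Peers × 15 or 20 × 12 (120 per arm), visits at 0, 6 and 12 weeks coded 0, 1, 2. Assumed, because the documents give no values: Peer intercept variance 0.05, participant variance 0.45, residual variance 0.50, and ICC of change within Peer (ρ) from 0 to 0.10.

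1. The variance of one participant's fitted slope is 0.50/Σ(t − mean t)² = 0.50/2 = 0.25. With Peer and participant intercepts, the model's SE for arm-by-time is √(2 × 0.25/120) = 0.0645. Peer intercept variance does not appear: raising it from 0 to 1.0 leaves 0.0645.
2. For an arm main effect without interaction (16 Peers), SE = √{2 × [Peer variance/8 + (0.45 + 0.50/3)/120]}. This is 0.101 at Peer variance 0 and 0.510 at 1.0, so here the Peer effect does count.
3. Let the Peer slope variance be 0.25ρ/(1 − ρ). The true SE of arm-by-time is √{2 × [0.25/120 + slope variance/8]}. At ρ = 0.05 this is √{2 × [0.002083 + 0.01316/8]} = 0.0863, and the nominal 5% test rejects 2 × [1 − Φ(1.96 × 0.0645/0.0863)] = 14%.
4. Without a participant term, participant variance falls into the residual (0.45 + 0.50 = 0.95). The model's SE becomes √(2 × (0.95/2)/120) = 0.0890, which is too large when ρ is small.

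| ρ | True SE, 16 × 15 | Type I error, Peer + participant intercepts (16 × 15; 20 × 12) | Type I error, Peer intercept only (16 × 15; 20 × 12) |
|---|---|---|---|
| 0 | 0.0645 | 5.0%; 5.0% | 0.7%; 0.7% |
| 0.01 | 0.0693 | 6.8%; 6.4% | 1.2%; 1.1% |
| 0.02 | 0.0738 | 8.6%; 7.9% | 1.8%; 1.5% |
| 0.05 | 0.0863 | 14.3%; 12.5% | 4.3%; 3.4% |
| 0.10 | 0.1054 | 23.0%; 19.9% | 9.8%; 7.7% |

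**Linear model after 20% attrition.** 240 × 0.80 = 192, which is 16 × 12, or 192/20 = 9.6 per Peer, taken as 9. Null simulations of change from T1 to week 6 used a continuous score, baseline Peer ICC 0.05, ICC of change 0.02–0.10 and within-person correlation 0.3–0.7 (all assumed). Over both sizes and repeated runs, a nominal 5% test rejected:

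- Peer intercept only: 0.1–14.1%, and below 5% in 6 of 9 settings at each size. The top of the range needs ICC of change 0.10 together with within-person correlation 0.3.
- Peer and participant intercepts: 5.9–19.7%.
- t-test on Peer mean changes: 4.3–5.8%.

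Two versions with a Peer-by-visit random effect were run at 16 × 12 with a normal reference. Added alone, it gave 0.2–8.6%. With a participant intercept as well, it gave 5.2–9.5%.

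**Logistic model.** 16 × 15, two visits, Peer intercept fitted, 500 runs per setting, no within-person correlation generated. As the Peer SD goes from 0.2 to 0.8 on the logit scale, the median arm-by-time SE goes from 0.464 to 0.466, so cancellation is near but not exact. With Peer-by-time SD 0.416 or 0.6, the fitted SE stays at 0.461 while the estimates vary with SD 0.519 or 0.542. Type I error is about 8% or 9%, with simulation error of about 1 point.

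**The case against.** The plan says only that Peers are a random effect. A reader might infer that it commits to an intercept and nothing else. It does not say so, and a Peer slope is not ruled out. What can be said is that no Peer-by-time term is specified.

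A reader might also infer that the randomised unit vanishes from the error of every comparison. It does not. The listed model has arm, Peer and time, with no interaction; its arm effect is a main effect, and Peer variance enters its SE (0.101 to 0.510 above). The point needs an arm-by-time contrast. That contrast is the natural meaning of a comparison between arms over time, but it is not written out.

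The higher error rates require a participant intercept that the plan does not name, although repeated-measures models ordinarily have some within-person term. As literally worded, the test is conservative in most settings tried, because the absent participant term partly offsets the absent Peer-by-time term.

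Finally, delivery is partly standardised, project meetings are weekly, and the setup section describes private communities by arm, while the recruitment section mentions Peer Leaders' own Facebook groups. Variation in response between Peers is plausible but not shown. The study is primarily a feasibility study, and its power statement concerns week-6 proportions.

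All of this limits the claim. It does not remove it: the stated structure, applied to the stated over-time comparison, has no term for Peer-level variation in change.

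**Conclusion.** The point holds for the arm-by-time contrast, on the ordinary reading of the Peer effect as an intercept. Cancellation is exact in the balanced linear model and nearly so in the logistic one.

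The size rests wholly on assumed variances and ICCs. At the sizes left after attrition, a nominal 5% test rejects about 0.1–14% with a Peer intercept only and about 6–20% with a participant intercept added. The logistic settings gave about 8–9%.

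The documents do not support a claim that the planned test is simply anti-conservative; its direction depends on whether a participant term is fitted. Repairing only the participant term, however, put the over-time test above 5% in the settings simulated. This is a specification that should be changed before analysis, not a defect in the data to be collected.

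**What to change.** Write out the arm-by-time (visit) term as the over-time comparison. Then do one of the following:

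- (a) Compute each Peer's mean change from T1 and compare arms by a t-test on the number of Peers minus 2 degrees of freedom (14 with 16 Peers, 18 with 20). This held about 5% in the simulations.
- (b) Fit participant and Peer-by-time random effects together, with small-sample degrees of freedom based on the number of Peers. Adding the Peer-by-time term alone is not enough, and with a normal reference the fuller model still rejected up to 9.5%. The version with Peer-based degrees of freedom was not simulated, so (a) should stand as the fallback if (b) cannot be estimated with 16–20 Peers.

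The cost is a wider interval where the present one is too narrow. No new data are needed.

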3. **Peers will actively recruit online** within their pre-existing social networks using text messages, brief videos, and picture graphics, using whichever mode is deemed appropriate. These recruitment advertisements will be co-developed by the Peers and investigators. Peers will then post the designated messages to their online social networks.
4. **In addition to recruitment lead by peers**, the research team will use the a study Facebook profile to buy ads on Facebook to outreach to potential participants. The ads will be targeted to 18-29 year old men who live in New York City, who are interested in Men, Men and Women or Unspecified, and who identify as Latino, Hispanic, Black or African American. Examples of the Facebook Ads can be found in the Participant Recruitment File. We will assign participants randomly with equal number to the Facebook groups of Peers Leaders who are having trouble with recruitment.
5. All recruitment messages will have customized links (enabling tracking of recruitment method and online venue) that will then lead participants to a secure study information and screening page (which will be cross-compatible across devices, e.g. a computer, iPad, or other mobile device such as smart-phones). To prevent inappropriate participants from joining the study and not inadvertently discourage appropriate participants, we will not display specific eligibility requirement on the recruitment messages.
6. Due to technological advancements, the ads will be geographically limited to those potential participants accessing these sites from the New York or have indicated a New York address on their social media profile. We have used this approach in our recently completed *theSEXword* social media pilot. While we will not explicitly exclude individuals not living or working in the Bronx, the above methods will help limit issues with potential participants being accidentally excluded and inappropriately included. This will also help reduce the burden of questions participants need to answer in the screening page. This approach will enable us to obtain a diverse sample of YMCSM living or working in

the New York.

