Compensation: Participants will be given \$20, \$30, and \$40 and \$20 as incentives after completion of assessments at baseline (T1), 6 weeks (T2), and 12 weeks(T3), and post 36 weeks (T4) (respectively). The participants will be given the choice to receive their incentives either via e-codes, Amazon online-gift cards, or by receiving a Clincard.

Data Collection:

We will collect three general types of data: 1) online processes (e.g. referral source, # of platforms joined by each participant); 2) measures of engagement with intervention components (e.g. # of views, time spent online); and 3) measures of outcome and independent variables, collected through online surveys at the ~~four~~three time points (see Table 2). To help assess both degree of exposure to intervention components and possible contamination between the two conditions, the surveys at 6 weeks (T2), ~~and~~ 12 weeks (T3) will display random samples of study and non-study graphics and posts and ask participants if they recall seeing them, with E-PrEP materials embedded in the choices.^{106,119,141}

Table 2. Data Collection					
Measures	Week	0	6	12	36+
PrEP intention, use, knowledge, attitudes		x	x	x	x
Perceived PrEP attributes		x	x	x	
HIV testing, risk behaviors		x	x	x	
Peer affinity and network data		x	x	x	

Table 2. Data Collection					
Measures	Week	0	6	12	36+
PrEP intention, use, knowledge, attitudes		x	x	x	x
Perceived PrEP attributes		x	x	x	
HIV testing, risk behaviors		x	x	x	
Peer affinity and network data		x	x	x	
Sociodemographic Factors		x			
Sexual Orientation		x			
Healthcare access		x	x	x	
Substance use		x	x	x	
Perceived risk, stigma		x	x	x	
Social media engagement		x	x		
Intervention exposure			x	x	

Data Security:

In order to securing information over the Internet and social media, and protecting participant data, an electronic, password protected and encrypted system will be developed to store analyses, and social media activity will remain private to study participants.¹⁶⁴ Research participants will be informed of how communications are recorded and stored during the online informed consent process. Due to the ever-changing and evolving nature of privacy issues on social media sites, we will review privacy settings for all social media study sites at least every four weeks and adjustments will be made to the study sites as necessary.

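### The sensitivity analysis meant to deal with intra-cluster correlation (outcomes against network size and Peer affinity) neither measures nor reliably corrects clustering by Peer, and no Peer-level check with a small-sample method takes its place

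*Combined protocol and SAP*

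**What the plan says.** Methods, Participants, sets the design: "The 16-20 peers will be randomized 1:1 to either E-PrEP or BxNow (control condition"), and "Each Peer will recruit approximately n=15 participants". Section I.1.2 gives 16 Peers.

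The Analytic Plan contains four things that bear on clustering:

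- At each time point the primary outcome, intention to use PrEP, is examined with an ordinary two-sample test of proportions. No adjustment for Peer is mentioned.
- Outcomes are compared across subgroups, and the referring Peer is one of the grouping variables.
- The between-arm models over time are mixed-effects models with arm fixed and Peer random. The later covariate models are also mixed-effects.
- The one sentence that names the problem reads: "To overcome possible limitations due to intra-cluster correlations, we will include a modified sensitivity analysis that examines outcomes in relation to" each participant's network size and felt closeness to the Peers.

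Table 2 (Data Collection) lists "Peer affinity and network data" at weeks 0, 6 and 12. Recruitment, item 4 (Procedures for General Participants), adds Facebook advertising: "In addition to recruitment lead by peers", people who answer the advertisements are randomly placed in the groups of Peers who are struggling to recruit.

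The Power Analysis gives "a sample size of 220, accounting for up to 20% attrition", which "will provide 80% power to detect an effect size of 20% in E-PrEP vs. 5% in BxNow". It states no ICC or design effect.

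**The concern.** Participants are correlated because they share a Peer: the same person writes the posts and runs the group. Network size and affinity are measured on the participant. Relating outcomes to them yields no ICC and does not widen a standard error that was computed as if participants were independent. It also does not show what happens to the arm difference when one influential Peer is removed. If the analysis has no Peer term, the clustering remains. If it has one, it is the main model with two more covariates, not a check on that model.

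Affinity is also a weak stand-in for cluster membership. People recruited by advertisement share a Peer without necessarily knowing that Peer beforehand. The sentence does not say which of the three affinity measurements is used, and those at weeks 6 and 12 follow exposure to the arm.

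What is at stake is the claim the report could make. It could present clustering as dealt with by an analysis that cannot do so, while the quantity that a later trial most needs, the ICC, goes unreported.

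**Working it through.** **Inputs.** From the documents: 20% v 5% at 6 weeks, 80% power, two-sided 0.05, 220 with up to 20% attrition, 240 planned, 16-20 Peers. Assumed, because the documents give no value: ICC of 0.02, 0.05 and 0.10.

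**1. The plan's own figure.** With mean proportion 0.125:

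n = [1.960 x sqrt(2 x 0.125 x 0.875) + 0.842 x sqrt(0.20 x 0.80 + 0.05 x 0.95)]^2 / 0.15^2 = 75.1 per arm.

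With continuity correction: (75.1/4) x [1 + sqrt(1 + 4/(75.1 x 0.15))]^2 = 87.95, so 88 per arm and 176 in all. Then 176/0.80 = 220, the stated number. It is reproduced exactly by a formula for individual randomisation, that is, with a design effect of 1. The plan does not name its formula; without the continuity correction the total would be 190.

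**2. A test that ignores Peer.** From 240 enrolled, 240 x 0.80 = 192 evaluable, or 192/16 = 12 per Peer. The design effect is DE = 1 + (12 - 1) x ICC, and the true two-sided error rate is about 2 x [1 - Phi(1.96/sqrt(DE))].

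| Assumed ICC | DE | Error rate |
|---|---|---|
| 0.02 | 1.22 | 7.6% |
| 0.05 | 1.55 | 11.5% |
| 0.10 | 2.10 | 17.6% |

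This applies to the planned two-sample test at each time point, if it compares the arms.

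**3. Does adjusting for network size and affinity help?** Simulated null trials, 16 Peers x 12. The first, second and last rows use a binary outcome (beta-binomial, 20% in both arms, 3,000 trials per ICC). The two middle rows use a continuous outcome; the half-share row spans separate set-ups.

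| Analysis | ICC 0.02 | ICC 0.05 | ICC 0.10 |
|---|---|---|---|
| Unadjusted | 7.8% | 12.3% | 17.4% |
| Two covariates, no Peer term; covariates carry none of the Peer variance | 7.7% | 12.2% | 17.5% |
| Same, affinity carries half | 6.6-6.7% | 8.8-10.8% | 12.6-14.7% |
| Same, affinity carries all | 4.8% | 4.4% | 4.7% |
| Peer-level t-test | 5.0-5.5% over the three ICCs | | |

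When the covariates are unrelated to Peer, the adjustment changes nothing. When affinity carries half of the Peer variance, part of the excess remains. The excess goes only if affinity explains all of it.

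**4. The planned type of model.** A random-intercept logistic model with Peer random and the usual z-test rejected in 4.8-9.5% of null trials (1,000 trials per cell, proportions 0.1-0.5, ICC 0.02-0.10). The simulation error near the top of that range is sqrt(0.095 x 0.905/1000) = 0.9 percentage points. It is a single-time-point version of the planned repeated-measures model.

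**5. Cost of a Peer-level test.** Degrees of freedom are the number of Peers minus 2: 14 for 16 Peers (t = 2.14) and 18 for 20 Peers (t = 2.10). Against 1.96 the interval is wider by 2.14/1.96 = 1.09 or 2.10/1.96 = 1.07, so 7-9%.

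**The case against.** The strongest reply is that the plan already adjusts for clustering. Its between-arm models carry Peer as a random effect, the standard adjustment; the ICC could be derived from that variance; and the sensitivity analysis only supplements those models. This stands. A reader might infer that the plan has no check on clustering at all, and the documents contradict that. A reader might also take 7-18% as the error rate of the planned analysis. It is not: nothing says the random effect is dropped, and the nearer figure for the planned type of model is about 5-9.5%.

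Two further readings go too far. One is that affinity says nothing about clustering: the protocol's diffusion model makes closeness to the Peer a plausible mechanism, and affinity could absorb some of the correlation. The other is that only post-exposure affinity would be used: Table 2 collects it at week 0 too.

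The comparison by referring Peer should make an outlying Peer visible. It is descriptive, though: Peers are nested in arm, so it neither adjusts nor re-estimates the arm effect.

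Finally, the Power Analysis puts feasibility and an effect estimate for a later application first, so strict error control matters less here. That lowers the weight of the point but does not remove it, because the interval around that estimate and the size of the next trial both depend on the ICC.

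**Conclusion.** The point holds in limited form. The sensitivity analysis cannot do the job its sentence assigns to it: it neither estimates between-Peer correlation nor reliably corrects for it, and it cannot show the influence of a single Peer. The random effect for Peer covers much of the ground, but it is the main model rather than a check on it, and no small-sample method is stated for 8-10 Peers per arm. ICC reporting and a Peer-level re-estimate are also missing, and the test at each time point leaves Peer out.

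The sizes rest on assumed ICCs of 0.02-0.10, equal Peer groups and 16 Peers, the low end of the planned range. With more Peers, smaller groups or a smaller ICC, the excess shrinks. This should be changed, but it does not invalidate the plan.

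**What to change.** Replace the sentence in the Analytic Plan with three items:

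1. A Peer-level sensitivity analysis. Compare the Peers' proportions or mean scores between arms by a t-test on (number of Peers minus 2) degrees of freedom, or by permuting the arm labels over Peers.
2. The arm effect re-estimated leaving out each Peer in turn.
3. The estimated Peer ICC with its confidence interval, for sizing the later trial.

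Keep network size and baseline (T1) affinity as exploratory analyses, and do not describe them as a correction for clustering.

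No new data are needed. The cost is a few lines of analysis and a Peer-level interval 7-9% wider than one using 1.96 with the same standard error.
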